CooperVision™

Study Implementation document: Protocol

CLINICAL EVALUATION OF BIOFINITY MULTIFOCAL TORIC CONTACT LENSES

Sponsor Study Code: CV-18-11
Version Number: 1.0
Implementation document Date: 21 Feb 2018
Sponsor Company: CooperVision, Inc.
Document Type: Protocol
Study Category: [REDACTED]
Clinical Sites: [REDACTED]
Site Protocol Number: C17-634

Study Sponsor Representative: _____ **Date:** _____
[REDACTED]

CooperVision Sponsor Management: _____ **Date:** _____
[REDACTED]

Site Principal Investigator: _____ **Date:** _____
[REDACTED]
[REDACTED]

Confidential

TABLE OF CONTENTS

1	Introduction	5
2	Study Objective	5
2.1	Study Hypothesis.....	5
3	Study Design	5
4	Ethics Review / Statement of Compliance	6
4.1	Relevant Standards / Guidelines.....	6
4.2	Institutional Review Board.....	6
4.3	Informed Consent	6
5	Clinical Trial Registration	7
6	Potential Risks and Benefits to Human Subjects	7
7	Materials and Methods	8
7.1	Subjects	8
7.2	Study Materials	9
7.3	Visit Schedule and Procedures	11
8	Adverse Event Reporting	16
8.1	Adverse Event Definitions	16
8.2	Procedures for Adverse Events.....	18
8.3	Reporting Adverse Events.....	18
8.4	Discontinuation from the Study	19
9	Device Malfunctions	19
10	Statistical Analysis	20
10.1	Statistical Plan	20
11	Data Quality Assurance	20
11.1	Study monitoring.....	20
11.2	Record keeping.....	21
11.3	Record retention	21
11.4	Data Entry / Data Management.....	21
11.5	Confidentiality	22
11.6	Publication	22
12	Study Costs	22

DOCUMENT CHANGE HISTORY

Version	Originator	Description of Change(s)	Date
1.0	[name]	Original Protocol	21 February 2018

1 Introduction

CooperVision, (CVI) is extending the power range of the commercially available Biofinity silicone hydrogel contact lenses to include multifocal toric silicone hydrogel contact lenses (Biofinity MFT).

This study is to evaluate the clinical performance of the Biofinity MFT lenses.

2 Study Objective

The objective of this non-dispensing clinical study is to compare the clinical performance of Biofinity Multifocal Toric (BF MFT) with Proclear Multifocal Toric (PC MFT) contact lenses.

The primary variable of interest is:

- Visual acuity (VA)

The secondary variable of interest is:

- Subjective assessments of visual performance

2.1 Study Hypothesis

The study hypothesis is that the Biofinity Multifocal Toric lenses will not be clinically inferior to Proclear Multifocal Toric lenses.

3 Study Design

This non-dispensing, subject masked, randomized, bilateral crossover study will compare the clinical performance of Biofinity Multifocal Toric contact lenses.

Up to 20 subjects, who have worn soft contact lenses in the last six months, will be enrolled.

This study will be composed of two parts. Part A will involve a screening/baseline visit for the determination of subject's contact lens prescription based on their spectacle refraction. With the

information obtained from Part A, Biofinity Multifocal Toric and Proclear Multifocal Toric contact lenses will be made to order on a per-patient basis for use in Part B to assess the clinical performance of the lenses.

Subjects must be able to participate in both parts of the study; Part A of the study will last approximately 1-2 hours duration and Part B will last approximately 3-4 hours duration.

4 Ethics Review / Statement of Compliance

4.1 Relevant Standards / Guidelines

This implementation document has been developed in accordance with the following:

- ISO 14155 Clinical Investigation of Medical Devices for Human Subjects
- 21 CFR 812.2(b) Investigational Device Exemption – Abbreviated Requirements
- ISO 11980 Contact Lens and Lens Care products – Guidance for Clinical Investigations
- ICH Harmonized Tripartite Guideline for Good Clinical Practice
- Declaration of Helsinki

4.2 Institutional Review Board

This study will be conducted in accordance with Institutional Review Board regulations (U.S. 21CFR Part 56.103) or applicable IEC regulations. Copies of all IRB/IEC correspondence with the investigator/sponsor will be kept on file.

The conduct of this study will be approved by The University of Manchester committee on the ethics of research on human beings (hereafter referred to as Manchester UREC) prior to commencement.

4.3 Informed Consent

Informed consent shall be obtained in writing from the subject and the process shall be documented before any procedure specific to the clinical investigation is carried out.

5 Clinical Trial Registration

This study will be registered with ClinicalTrials.gov in accordance with Section 801 of the Food and Drug Administration Act (FDAA) which mandates the registration of certain clinical trials of drugs and medical devices.

6 Potential Risks and Benefits to Human Subjects

There might not be direct benefits to the subjects in this study. However, participation in a study may contribute to scientific research information that may be used in the development of new contact lens products. In addition, subjects will receive an examination of the front part of their eyes and may have the opportunity to try a different type of soft contact lenses and/or different lens care products at no cost to them.

The investigational contact lenses used in this study are CE marked and intended for daily wear (NOT extended wear) with usage of up to four hours only, in contrast to the average wearing time of 10-16 hours for daily wear lenses. In addition, this study is a non-dispensing study, meaning the lenses are not dispensed to subjects to take home and lens wear will be monitored closely by the investigators.

This study is considered to be a non-significant risk study based on United State Food and Drug administration (FDA) and International Standards Organization (ISO) guidelines due to no potential of serious risk to the health, safety, or welfare of a subject.

Complications that may occur during the wearing of contact lenses include discomfort, dryness, aching or itching eyes, excessive tearing, discharge, hyperemia and variable or blurred vision. More serious risks may include photophobia, iritis, corneal edema and eye infection. Although contact lens-related infections are very infrequent, the possibility does exist. The incidence of infection due to day-wear soft lenses is 0.035%. An infection will usually occur only in one eye. This risk is assumed by 35 million Americans who currently wear contact lenses.

Routine clinical procedures including auto-refraction, auto-keratometry, visual acuity, anterior ocular health assessment, and contact lens fitting may be used. In addition, high magnification imaging of the lens fit may be made using 35 mm or digital cameras.

7 Materials and Methods

7.1 Subjects

Up to twenty subjects will be needed to complete the study. Each subject will be given a unique ID number. Additionally, all subjects must meet the study inclusion and exclusion criteria listed below. Potential subjects will be identified from the investigators' clinic database records and/or will be actively recruited by advertisements circulated at the investigational sites approved by the appropriate IRB.

Inclusion Criteria

A person is eligible for inclusion in the study if he/she:

- Has had a self-reported oculo-visual examination in the last two years.
- Is aged 40–75 years, inclusive and has full legal capacity to volunteer.
- Has read and understood the participant information sheet.
- Is willing and able to follow instructions and maintain the appointment schedule.
- Is able to participate in Parts A and B related to this work.
- Has a contact lens spherical prescription between +10.00 to -10.00D (inclusive).
- Has an Add component to their spectacle refraction (between +0.75 and +2.50DS).
- Has astigmatism between -0.75 and -5.75DC (based on the vertexed ocular refraction in each eye).
- Can be satisfactorily fitted with the study lenses.
- Is correctable to a visual acuity of 20/40 (0.30 logMAR) or better (in each eye) with their habitual vision correction or 20/25 (0.10 logMAR) best-corrected.
- They have successfully worn soft contact lenses in the last six months
- Has clear corneas and no active ocular disease.
- Has not worn lenses for at least 12 hours before the examination.
- Has an up-to-date pair of spectacles.

Exclusion Criteria

A person will be excluded from the study if he/she:

- Has never worn contact lenses before.
- Has any systemic disease affecting ocular health.

Confidential

- Is using any systemic or topical medications that will affect ocular health.
- Has any ocular pathology or severe insufficiency of lacrimal secretion (moderate to severe dry eyes) that would, in the opinion of the investigator, affect the wearing of contact lenses.
- Has persistent, clinically significant corneal or conjunctival staining using sodium fluorescein dye that would, in the opinion of the investigator, be problematic for their participation in the study.
- Has any clinically significant lid or conjunctival abnormalities, active neovascularization or any central corneal scars.
- Is aphakic.
- Has undergone corneal refractive surgery.
- Has a history of anaphylaxis or severe allergic reaction.
- Has diabetes or an infectious or immunosuppressive disease which could contraindicate contact lens wear or pose a risk to the investigator.
- They are pregnant or breast-feeding.
- Is participating in any other type of eye-related clinical or research study.

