7.3.1 Screening/Baseline Visit (Part A)

The subjects should attend wearing their spectacles, not having worn their own contact lenses for a minimum of 12 hours prior to this visit.

Procedures to be Performed

The following evaluations will be performed to assess eligibility according to the Inclusion and Exclusion Criteria at the baseline visit only:

The following evaluations will be performed on all subjects:

1. The subject will be required to read and sign an Informed Consent Form prior to enrolment. When the subject has signed the consent form, the subject will then be considered to be enrolled in the study
2. Subject demographics (age, sex, medications, allergies)
3. Contact lens wearing history including:
 - Habitual lenses, modality, average wear time and comfortable wear time
4. Auto-refraction and Auto-keratometry measures will be recorded
5. Pupil size measurements (OD, OS) (high and low illuminationat distance (equivalent to 6M) and near (40cm)
6. HVID measurement
7. Baseline distance high contrast logMAR visual acuity (OD, OS) with spectacles or habitual Rx in phoropter or trial frame
8. Monocular sphero-cylindrical refraction (D) followed by binocular balance (endpoint is the most plus or least minus that gives the best binocular distance visual acuity)
9. Near addition as determined by NRA/PRA/BCC (D)

10. Dominant eye test (sensory): the dominant eye will be determined using the +2.00D blur test
11. Visual acuities with best correction:
 - Best-corrected high contrast, high illumination*, distance (equivalent to 6M), logMAR acuity (OD, OS and OU) (natural pupil)
 - Best-corrected high contrast, high illumination*, near (40cm), logMAR acuity (OD, OS and OU) (natural pupil)

*High room illumination: Overhead lights on = 300-600 lux
12. Slit lamp biomicroscopy will be assessed according to the guidelines set out in the CVI Grading scales (Appendix 1)
13. Saline Rinse
14. Confirm subject meets the inclusion/exclusion criteria
15. The information required from the spectacle refraction includes:
 - Spectacle refraction (vertex corrected assuming a 15 mm vertex distance) (D)
 - Keratometry readings (D)
 - Dominant eye (sensory)
 - Add power (D)
16. The information from #15 above will be used to determine the contact lens prescription based on the fitting guides (Appendix 2).
17. The site will send the contact lens prescriptions to the Sponsor who will then order the contact lenses.

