7.3.5 Summary of Visits and Procedures

Table 2 summarizes the visits and procedures for the study.

Table 2: Summary of Visits and Procedures

	Screening/ Baseline visit	Lens fitting and exit visit
Informed Consent	✓	
Meet inclusion/exclusion criteria	✓	✓
Demographics	✓	
History at baseline	✓	✓
VA with spectacles or refraction	✓	✓
Auto-refraction & keratometry	✓	
Pupil size / HVID	✓	
Sphero-cylindrical refraction	✓	

Best corrected (sphero-cyl) logMAR VA monocular and binocular	✓	
Add determination	✓	
Dominant eye test (+2.00 blur test)	✓	
Instillation of lens at office	–	✓
██████████	█	█
logMAR VA with contact lenses	–	✓
██████████		█
Slit lamp findings	✓	✓
██████████ ██████████	█	█
Exit study		✓

8 Adverse Event Reporting

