10.1 Statistical Plan

Summary statistics will be produced (e.g. mean, standard deviation). Paired t test will be used to compare slit lamp biomicroscopy, lens fit and subjective scores between study lens types. Repeated Measures Analysis of Variance (ANOVA) or paired analysis will be used to compare the variables between study visits. The critical alpha level for statistical significance will be set at $p \leq 0.05$, with adjustment for multiple comparisons.

All participants who were evaluated will be used in the analysis. In the event of missing data, individual data points will be excluded in the analysis and not extrapolated from the collected data.

11 Data Quality Assurance

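### Does the inclusion criterion on satisfactory fit let subjects be excluded on an outcome after randomised lens insertion?

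*Combined protocol and SAP*

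**What the plan says.** - **Criterion (section 7.1).** One inclusion criterion is that the subject "Can be satisfactorily fitted with the study lenses". The visible text does not define a satisfactory fit.
- **Timing in the text (section 7.3.1).** The Part A evaluations are done "to assess eligibility according to the Inclusion and Exclusion Criteria at the baseline visit only". Step 14 is "Confirm subject meets the inclusion/exclusion criteria". The prescription is worked out at step 16, and at step 17 "The site will send the contact lens prescriptions to the Sponsor who will then order the contact lenses".
- **Lens supply (section 3).** The "contact lenses will be made to order on a per-patient basis for use in Part B". Section 7.3.3.1 has the first pair inserted at Part B in randomised order.
- **Timing in the table (section 7.3.5, Table 2).** The row "Meet inclusion/exclusion criteria" is ticked at the baseline visit and again at the second visit.
- **Analysis (section 10.1).** Lens fit is compared between lens types by paired t test. On the analysis set: "All participants who were evaluated will be used in the analysis". Missing data lead to the loss of individual data points.

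**The concern.** Actual fit cannot be seen until a lens is on the eye, and no trial-lens fitting is listed at Part A. If the criterion means observed fit, it can be applied only at Part B, after the randomised sequence has begun, and the second tick in Table 2 seems to allow that. Fit is also an outcome, so a subject could become ineligible because of how the test lens behaved.

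In a crossover, excluding a subject removes the paired difference. If poor fit were commoner with the test lens and also lowered acuity, the lost pairs would be the unfavourable ones. With a non-inferiority hypothesis, the bias would run towards the conclusion the sponsor hopes for.

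**Working it through.** The plan gives no figure on this point: no poor-fit rate, no acuity margin, and no derivation behind the ceiling of 20 subjects. The check is therefore mainly one of sequence.

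**1. Can the criterion be judged at Part A?** Yes. By step 14 the site has keratometry (step 4), iris diameter (step 6), refraction (step 8), add (step 9), eye dominance (step 10) and slit-lamp findings (step 12). Table 1 gives the lens parameters: base curve 8.7 mm for the test lens against 8.4 or 8.8 mm for the control, and diameter 14.5 against 14.4 mm. The prescription is formally derived at step 16, but its inputs are already measured. The wording asks whether the subject can be fitted, which is naturally a prospective judgement.

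**2. Does the second tick in Table 2 imply exclusion after insertion?** Not necessarily. Section 7.3.2 opens Part B with a 12-hour lens-free requirement, a check for changes in history, spectacle acuity and slit lamp, all before any study lens is inserted. That is a natural place for a second eligibility check. The phrase in section 7.3.1 can also be read as limiting the listed evaluations to baseline. Table 2 fits that reading: refraction, keratometry, pupil size, add and dominance are ticked at baseline only.

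**3. Does any visible text remove a poorly fitted subject?** No. Section 8.4 allows discontinuation in the subject's best interest and does not mention fit. Section 10.1 keeps evaluated participants and drops missing points, not people.

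**4. Would such a subject contribute the primary variable?** On the listed order, yes. Lenses settle for at least 15 minutes (section 7.3.3.1), and acuity is then step 1 of section 7.3.3.2, before over-refraction. A subject with a poor fit has acuity recorded first and is evaluated in the ordinary sense.

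**5. How large would the effect be if exclusion did occur?** All inputs here are assumptions. Let k of 20 subjects fit poorly with the test lens only, each losing d logMAR, with no difference in the rest. The mean over all 20 is k × d / 20, and excluding the k subjects makes it 0.

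| k | d = 0.10 | d = 0.20 | subjects left |
|---|---|---|---|
| 1 | 1 × 0.10 / 20 = 0.005 | 1 × 0.20 / 20 = 0.010 | 19 |
| 2 | 2 × 0.10 / 20 = 0.010 | 2 × 0.20 / 20 = 0.020 | 18 |
| 4 | 4 × 0.10 / 20 = 0.020 | 4 × 0.20 / 20 = 0.040 | 16 |

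If poor fit is equally common with both lenses and costs the same acuity, the expected bias is zero. If it is commoner with the control, the sign reverses. The documents state no rate for either lens.

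The chance of at least one poor fit among 20 is 1 − (1 − q)^20. For assumed per-subject rates q of 2%, 5% and 10% this is 33%, 64% and 88%. A case could well arise, but under section 10.1 as written it stays in the analysis.

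**The case for a change.** The best argument for a change is that the plan never says which reading of the criterion applies. Sphere, cylinder and add ranges are already separate criteria, so a reading based only on lens parameters looks nearly redundant. Eligibility is confirmed two steps before the prescription is derived. Lens-specific poor fit is credible, since the test lens has one base curve and the control two. Masking is described for the subject only, so an investigator who may know the lens could apply an undefined standard after insertion. The term for who is analysed is also undefined, and a lens removed before acuity was measured would leave a missing point and so a lost pair.

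Part of this stands. The two undefined terms and the loose fit between section 7.3.1 and Table 2 are real, and the masking point is fair. The redundancy argument is weaker: base curve and diameter, judged against keratometry and iris diameter, are not covered by the power ranges, so the criterion still does work at Part A. The lost-pair route requires departing from the listed order of assessments. The rest of the lens-fitting part of section 7.3.3 is redacted and Appendix 2 is not shown, so the lack of a definition or handling rule in the visible text cannot be counted against the plan.

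**Conclusion.** The sequence is as described, but the harm is not shown. Outcome-based exclusion would require reading the criterion as observed fit, applying it after insertion, and then dropping the subject despite section 10.1. The visible plan directs none of these. Followed as written, a poorly fitted subject has acuity measured, counts as evaluated and stays in, so the hidden deficit is nil.

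The range of 0.005 to 0.040 logMAR rests wholly on assumed numbers of poor fits, assumed acuity losses, failure with the test lens alone and an exclusion rule that is not there. It is not an estimate of bias in this trial. It also cannot be set against a margin, because the documents state none.

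This conclusion assumes that the criterion is judged prospectively at Part A, that acuity is taken in the listed order, and that evaluated has its ordinary meaning. Each is the natural reading. What is left is a gap in wording that analysts would fill sensibly, and no change to the plan follows.

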7.1.1 Subject Identification

Each subject will be given a unique ID number. Subject ID numbers will be assigned to the subjects sequentially and in ascending order, and will not be reused in the event of screen failure, subject dropout or discontinuation from the study.

7.2 Study Materials

7.2.1 Contact Lens

Subjects will be randomized to receive either the Test or Control lens as the first pair of contact lenses as per the randomization schedule. The lenses used in this study will be provided by the Sponsor.

Details of the CE marked contact lenses are shown in Table 1.

Table 1: Study lenses

	Lens 1	Lens 2
Name	Biofinity Multifocal Toric	Proclear Multifocal Toric
Manufacturer	CooperVision	CooperVision
Material	Comfilcon A	Omafilcon B
EWC (%)	48%	62%
Base Curve (mm)	8.7	8.4 / 8.8
Diameter (mm)	14.5	14.4
Spherical powers (DS)	+10.00 to -10.00 (0.50 steps after $\pm 6.50D$)	+20.00 to -20.00 (0.50 steps after $\pm 6.50D$)
Cyl Powers (DC)	-0.75 to -5.75 (0.50 steps)	-0.75 to -5.75 (0.50 steps)
Axis (°)	5 to 180 (5 degree steps)	5 to 180 (5 degree steps)
Add (D)	+1.00, +1.50, +2.00, +2.50 (D & N)	+1.00 to +4.00 (D & N)

7.2.2 Contact Lens Care

No contact lens care is required for this study as lenses are to be worn in the clinic only.

7.2.3 Storage of Lenses

The study materials must be stored in a secured area. All lenses should be stored at controlled room temperature (59-86°F, 15-30°C).

7.2.4 Clinical Supply Inventory

All lenses will be supplied by the Study Sponsor. The investigator must keep an accurate account of the study product during the study. A detailed inventory must be completed for study supplies. The study supplies are to be used in accordance with the implementation document by subjects who are under the direct supervision of an investigator.

7.2.5 Disposal of Consumables

This study dispenses consumables (lenses) to participants for use during the study. All unused and used materials will be returned to the Sponsor at the end of the study unless the investigator is otherwise directed by the study Sponsor. All worn lenses will be collected at the completion of the study in screw top contact lens cases filled with either a suitable multi-purpose solution or saline.

7.2.6 Masking and Control of Study Materials

The contact lens coding will be masked to the subject. Masking to the subject will be achieved by minimising the exposure to the device label.

7.2.7 Ordering and Accountability of Study Materials

The test and control lenses will be provided by the sponsor. The investigator must complete an accurate account of the study product at the completion of the study. A detailed inventory must be completed for study supplies.

7.3 Visit Schedule and Procedures

There will be a minimum of two scheduled visits as follows:

7.3.1 Screening/Baseline Visit (Part A)

The subjects should attend wearing their spectacles, not having worn their own contact lenses for a minimum of 12 hours prior to this visit.

Procedures to be Performed

The following evaluations will be performed to assess eligibility according to the Inclusion and Exclusion Criteria at the baseline visit only:

The following evaluations will be performed on all subjects:

1. The subject will be required to read and sign an Informed Consent Form prior to enrolment. When the subject has signed the consent form, the subject will then be considered to be enrolled in the study
2. Subject demographics (age, sex, medications, allergies)
3. Contact lens wearing history including:
 - Habitual lenses, modality, average wear time and comfortable wear time
4. Auto-refraction and Auto-keratometry measures will be recorded
5. Pupil size measurements (OD, OS) (high and low illuminationat distance (equivalent to 6M) and near (40cm)
6. HVID measurement
7. Baseline distance high contrast logMAR visual acuity (OD, OS) with spectacles or habitual Rx in phoropter or trial frame
8. Monocular sphero-cylindrical refraction (D) followed by binocular balance (endpoint is the most plus or least minus that gives the best binocular distance visual acuity)
9. Near addition as determined by NRA/PRA/BCC (D)

10. Dominant eye test (sensory): the dominant eye will be determined using the +2.00D blur test
11. Visual acuities with best correction:
 - Best-corrected high contrast, high illumination*, distance (equivalent to 6M), logMAR acuity (OD, OS and OU) (natural pupil)
 - Best-corrected high contrast, high illumination*, near (40cm), logMAR acuity (OD, OS and OU) (natural pupil)

*High room illumination: Overhead lights on = 300-600 lux
12. Slit lamp biomicroscopy will be assessed according to the guidelines set out in the CVI Grading scales (Appendix 1)
13. Saline Rinse
14. Confirm subject meets the inclusion/exclusion criteria
15. The information required from the spectacle refraction includes:
 - Spectacle refraction (vertex corrected assuming a 15 mm vertex distance) (D)
 - Keratometry readings (D)
 - Dominant eye (sensory)
 - Add power (D)
16. The information from #15 above will be used to determine the contact lens prescription based on the fitting guides (Appendix 2).
17. The site will send the contact lens prescriptions to the Sponsor who will then order the contact lenses.
18. The subject will then be discharged and asked to return when lenses are available for Part B of the study. Subjects will be free to return to wearing their habitual lenses until the follow-on study begins. Study personnel will contact them to schedule Part B of the study upon lens arrival.

